4.1.1 Handling of Missing Data

This section describes the general handling of missing data. This includes data that would be meaningful for the analysis in terms of the study objectives but were not collected. The rules for handling the data that do not exist or are not considered meaningful for the analysis because of an intercurrent event, are described in Section 4.2.2.1. No imputation of missing assessments will be performed for the secondary and exploratory endpoints unless it is specified otherwise.

All data will be presented in the participant data listing as they are recorded on the Case Report Form (CRF), i.e., partially missing data will appear as such.

4.1.1.1 Polysomnography (PSG)

Several parameters of sleep quality will be measured by on-site PSG assessments performed at screening, week 4 and week 12 with each visit consisting of 2 consecutive nights. See Section 6.2.1 for the list and definition of sleep parameters as measured by PSG.

For the analysis of PSG parameters, the mean value of the 2 consecutive nights at each visit will be calculated. If a participant only had one PSG night for a given visit, the data from the one night will be used for the analysis.

Version 2.0 Page: 16 of 57

Further details regarding imputation rules for completely missing visits (i.e., no evaluable data from any nights) for WASO are described in Section 4.2.2.1. No imputation will be performed for other PSG parameters in case the visit is missing completely.

4.1.1.2 Sleepiz One+

Several parameters of sleep quality will be measured continuously at home and during the nights of the PSG assessments by the Sleepiz One + system from SCR-2 visit through to week 12/EoT visit. See Section 6.2.2 for the list and definition of sleep parameters as measured by Sleepiz One+.

No imputation of missing assessments will be performed for parameters measured by the Sleepiz One +.

4.1.1.3 Electronic Patient Reported Outcomes (ePROs)

There are two types of missing data for ePRO measures: missing data at the 'form' level and missing data at the 'item' level.

Form level missing refers to a participant missing an entire PRO assessment for a given time point (e.g., a given day (i.e., morning and evening) for the HFDD and a given week for the PROMIS SD SF 8b). In general, form level data may be missing due to participant's early withdrawal from the study, inability to evaluate an endpoint at a particular time point, or noncompliance.

By design of the eDiary, there will be no item level missing data for the respective ePRO questionnaires because the participants have to select an answer for an item in order to move on to the next item on the eDiary/electronic handheld device, with the exception for the eC-SSRS where the form can be submitted even if incomplete.

No imputation of missing assessments will be performed for any ePRO measures.

4.1.1.4 Adverse Events (AE) and Concomitant Medications (CM)

For computation of durations, i.e., time between start and end dates of certain events and concomitant medication intake, a complete date is necessary.

The following rule will be applied to impute partial missing start or end date of AE/CM:

An imputation range will be defined as the earliest possible date (lower range) and the latest possible date (upper range) of the occurrence of AE/CM. If AE/CM end date is available, this will be used as the latest possible AE/CM occurrence date in the imputation range.

If the start of study treatment date falls within imputation range, incomplete AE/CM start date will be imputed as the start of study treatment date. Otherwise, the partially missing AE/CM start date will be imputed to the earliest date of the imputation range. Completely missing start date will not be imputed and will be considered treatment-emergent for AEs and concomitant for CMs.

Partially missing AE/CM end date will be imputed as the latest possible date of AE/CM imputation range. Completely missing end date will not be imputed and presumed to be ongoing.

Version 2.0 Page: 17 of 57

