4.5.2 Adverse Events (AEs)

All AEs will be summarized using MedDRA (the current version at the time of analysis) PTs grouped by SOC.

Any AEs related to study procedures recorded after signing of informed consent but prior to randomization will be considered as pre-treatment AEs. AEs that occurred or worsened after the first dose of study intervention up to 14 days after the last dose of study intervention will be considered as treatment-emergent AEs (TEAEs). AEs that occurred 15 days after last dose will be considered as post-treatment AEs.

Partially missing onset AE date will be imputed following a worst-case approach as described in Section 4.1.1.4.

If the severity of a previously reported event worsens or if the relationship to study intervention/protocol required procedures changes, two separate events should be reported.

Worsening of an AE is defined as follows:

- AE intensity is worsened (e.g., moderate to severe)
- AE changed to a serious event
- AE ends with death

In case an AE starts before the date of last study intervention intake + 14 days and worsens after last study intervention intake +14 days, it will be considered as two AEs, a TEAE and a post-treatment AE.

In case of events with different intensity within a participant, the maximum reported intensity will be used. If the same event is reported as both unrelated and related to the study intervention within a participant, the event will be considered as related to study intervention. If the study intervention relationship is missing, the event will be considered as being related to the study intervention. For AEs, relationship to study intervention refers to elinzanetant and placebo only.

Overall summaries of the number of participants with pre-treatment AEs, TEAEs, and post-treatment AEs will be generated by study treatment.

The number of participants with the following AEs will be summarized by study treatment using PTs grouped by SOC:

- pre-treatment AEs
- post-treatment AEs

Version 2.0 Page: 36 of 57

- SAEs (includes both treatment-emergent and post-treatment)
- TEAEs, TEAEs of special interest, TEAEs resulting in discontinuation of study intervention, TEAEs by maximum intensity
- treatment-emergent study intervention related AEs, treatment-emergent study intervention-related AEs by maximum intensity, treatment-emergent study intervention-related AEs resulting in discontinuation of study intervention

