6.1.7 Prior, Concomitant and Post-Treatment Medication

For prior and concomitant medications, the following definitions apply:

- Prior medication: Medication taken before start of the study intervention intake, (regardless of when it ended).
- Concomitant medication: Medication taken during treatment period, i.e., between first and last study intervention intake (regardless of when it started or ended).
- Post-treatment medication: Start of medication is after last study drug intake.

Missing dates will be imputed as described in Section 4.1.1.4.

Prior, concomitant and post-treatment medication will be coded to Anatomical Therapeutic Chemical (ATC) classification codes according to the World Health Organization Drug Dictionary (WHO-DD, current version at the time of analysis). The number of participants taking prior, concomitant, post-treatment medication, and prohibited concomitant medications will be presented by study treatment and overall using ATC classes and subclasses.

Version 2.0 Page: 46 of 57

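### SAP 4.1.1.4 counts a medication with no start date as concomitant even when its recorded end date precedes the first dose, against the SAP's own definition (minor)

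*SAP*

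**What the plan says.** SAP 4.1.1.4 has two separate provisions for start dates.

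- **Partly known dates.** The imputation range is introduced this way: "The following rule will be applied to impute partial missing start or end date of AE/CM". A recorded stop date limits that range: "If AE/CM end date is available, this will be used as the latest possible AE/CM occurrence date in the imputation range". If the range contains the first day of treatment, the start is set to that day; otherwise it is set to the earliest date in the range.
- **No part of the date known.** "Completely missing start date will not be imputed and will be considered treatment-emergent for AEs and concomitant for CMs". Nothing is said about the end date.

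SAP 6.1.7 defines the classes by when the drug was taken. One reads: "Concomitant medication: Medication taken during treatment period, i.e., between first and last study intervention intake (regardless of when it started or ended"). The other reads: "Prior medication: Medication taken before start of the study intervention intake, (regardless of when it ended"). For incomplete dates it sends the reader back: "Missing dates will be imputed as described in Section 4.1.1.4". It then plans counts by arm of prior, concomitant and post-treatment drugs, and "prohibited concomitant medications will be presented by study treatment and overall using ATC classes and subclasses".

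For adverse events, SAP 4.5.2 defines treatment-emergent events as "AEs that occurred or worsened after the first dose of study intervention up to 14 days after the last dose of study intervention". The same section classes procedure-related events recorded between consent and randomization as pre-treatment.

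**The concern.** Treating an undated record as on-treatment is a sensible default when its timing is uncertain. Here the timing is not uncertain: if a drug was stopped before the first dose, it was not taken between first and last dose, whenever it began. The sentence in 4.1.1.4 ignores that information, although the preceding rule for partial dates uses it.

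Two sections of the SAP therefore give different answers for the same record. One programmer may follow the definition in 6.1.7 and another the rule in 4.1.1.4, and their tables will differ. At stake are the concomitant and prohibited-concomitant medication tables by arm, which readers use to judge whether other drugs could have influenced the sleep results. The trial produces records of the relevant kind by design: Protocol 4.1 withdraws women from prohibited drugs at the first screening visit where needed, and Protocol 6.9.1 asks for sleep therapies used in the 3 months before the second screening visit to be recorded.

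**Working it through.** The plan states no figure on this point. The check applies the rule as written to six date patterns and then repeats it with an end-date exception.

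**Inputs.** The rule is SAP 4.1.1.4 and the class definitions are SAP 6.1.7. The dates are hypothetical: first dose 1 MAR 2024, last dose 84 days later.

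| Start | End | 4.1.1.4 as written | With end-date exception |
|---|---|---|---|
| Missing | 31 JAN 2024 (30 days before first dose) | Concomitant | Prior only |
| Missing | 29 FEB 2024 (1 day before) | Concomitant | Prior only |
| Missing | 11 MAR 2024 (10 days after) | Concomitant | Concomitant |
| Missing | Missing | Concomitant | Concomitant |
| Year 2024 only | 31 JAN 2024 | Prior only | Prior only |
| Year 2024 only | 11 MAR 2024 | Concomitant | Concomitant |

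Rows 1 and 5 differ only in whether the start year is known. In row 5 the range runs from 1 JAN 2024 to the end date, 31 JAN 2024. It does not contain 1 MAR 2024, so the start becomes 1 JAN 2024 and the drug is prior. In row 1 no range is formed and the drug is concomitant. The exception changes rows 1 and 2 only. The two rows whose timing is open or clearly on treatment despite a missing start (rows 3 and 4) keep their class.

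**Direction of the error.** The classes in 6.1.7 overlap. A drug stopped before the first dose meets the definition of prior, and 4.1.1.4 does not remove it from that class. The error is an extra count in the concomitant tables, not a loss from the prior table.

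**Size per record.** With 39 women planned per arm (SAP 5), one misclassified woman adds 1/39 = 0.0256, about 2.6 percentage points, to her arm's row.

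**Adverse events.** Protocol 8.4.1 collects only procedure-related events before the first dose; other conditions arising then go to medical history. SAP 4.5.2 makes procedure-related events recorded before randomization pre-treatment. An undated procedure-related event that was recorded and resolved during screening is thus pre-treatment under 4.5.2 and treatment-emergent under 4.1.1.4. Outside that conflict there remains only a procedure-related event that ended before dosing, was not recorded until randomization or later, and has no part of its onset date.

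**Intercurrent events.** SAP 6.4.3 judges prohibited medication at each PSG night from intake and the impact duration after the last dose. It does not use the concomitant label. Taking a drug stopped on Day -1, a 2-week impact ends at about Day 14 and a 4-week impact at about Day 28, both before the Week 4 visit on Day 29. Impacts of 8, 12 and 24 weeks would end at about Day 56, 84 and 168 and could reach a PSG night, but that follows from the stop date and is the same with or without the sentence in 4.1.1.4.

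**The case against.** The strongest reply is that this is a cautious default with a narrow trigger. Day, month and year of start must all be missing while the end date is known and precedes dosing. Protocol 6.9 requires start and end dates to be recorded, and a year alone moves the record to the partial-date rule, which works. The affected drugs were stopped before the first dose, so their use cannot depend on the assigned arm and no systematic difference between arms is expected. SAP 6.3 adds manual review of prohibited drugs and a blinded review of the list, and SAP 4.1.1 lists data as recorded, so the stop date stays visible.

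Most of this stands, and it is why the point is minor. It does not remove the contradiction. Caution is not a reason to override a known stop date, and the reviews named do not amend the rule. An error balanced in expectation can also be visible by chance when one woman is about 2.6 points.

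A reader might go further and infer that washed-out drugs in general will appear as on-treatment use. The documents do not support that: drugs with even a start year and a pre-dose stop date are classed correctly. A reader might also infer that the treatment-emergent event endpoint is inflated by events that ended before dosing. SAP 4.5.2 supplies a competing rule for nearly all such events, so the text shows an inconsistency and not a certain miscount.

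**Conclusion.** The point holds for medications. SAP 4.1.1.4 labels a drug with a completely missing start date concomitant regardless of a pre-dose end date, contrary to SAP 6.1.7 and out of line with its own treatment of partial dates. The consequence is an overcount in descriptive tables: concomitant medication and, assuming that table uses the same label as its name implies, prohibited concomitant medication. For adverse events it is an inconsistency between 4.1.1.4 and 4.5.2 that would change few or no counts.

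The number of affected records is not in the documents and could be zero, so no total is offered; only the size per woman can be stated. It would be wrong to infer that the primary result is touched. Intercurrent events are set by intake and impact duration, so the primary estimand does not change. Severity: minor.

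**What to change.** In SAP 4.1.1.4, extend the sentence on completely missing start dates with: *unless the end date (complete, or the latest possible date if partial) is before the start of study treatment, in which case the medication is prior only and the AE is pre-treatment.*

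This keeps the cautious default wherever timing is open and brings 4.1.1.4 into line with 6.1.7 and 4.5.2. The cost is one clause in the SAP and one condition in each of the medication and adverse event derivations. No new data are needed.

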4.1.1.5 Other Missing Data

The date of permanent discontinuation of study medication will be collected in eCRF. In case of missing date, it will be determined based on last medication intake date before the discontinuation using available eDiary data.

4.1.2 Data Rules

Baseline: Unless otherwise specified, baseline is defined as the latest available valid measurement (including unscheduled measurements) on or before the start date of study treatment (for treated subjects) / randomization date (for randomized but not treated subjects). If the last observation available prior to randomization is the measurement from the screening visit, this would be used as the baseline value.

Change from baseline: To calculate the absolute change from baseline, the baseline value will be subtracted from the value under treatment/follow-up, i.e.,

Absolute change = post baseline value – baseline value.

Some parameters will be additionally analyzed as percent change defined as:

Percent change = [(post baseline value - baseline value) / baseline value] x 100.

Visit confirmation date for HF eligibility check: Refers to the date, as captured on the electronic handheld device, when the eligibility for inclusion criteria of ≥ 20 average weekly frequency of moderate to severe HFs was assessed.

Laboratory values <**X** or >**Y**: For laboratory values lower than a limit of detection X (reported as <X), half the value of X will be used for analysis (i.e., for values reported as "<X", "<X.XX", "<X.XX" or etc. the value for analysis will be derived by "X/2", "X.X/2", "X.XX/2", etc.).

Difference between 2 values <X will be assigned a value of 0. Ratio between 2 values <X will be assigned a value of 1.

For values which are higher than a limit of detection Y (reported as, >Y), the value of Y will be used for analysis.

Repeated measurements at the same date: For PROMIS SD SF 8b, ISI, GAD-7, PGI-S and PGI-C, if more than one entry on the same date for any pre- and post-baseline visit is available, then the first entry will be used and all observations will be presented in the data listings.

Start of treatment: Refers to the first drug intake and will be identified based on the 'Study Intervention' eCRF entry.

Stratification factor: The stratification factor average weekly frequency of moderate to severe HFs (including nighttime HFs) (see Section 1.2) will be assigned in the IRT system during randomization. The average weekly frequency of moderate to severe HFs is based on HFDD data and will be calculated using the 14 days prior to the visit confirmation date for HF eligibility check. A minimum of 11 days should be available for the calculation of the average weekly value. In case participants are incorrectly stratified, the actual stratification will be used in the analysis. The actual average weekly frequency of moderate to severe HFs will be the value calculated in the eDiary/electronic handheld device. If more than 10% of

Version 2.0 Page: 18 of 57

participants are incorrectly stratified, a sensitivity analysis may be performed using the assigned strata.

Study day 1: Defined as the day of start of treatment, or randomization day if participant did not take study treatment.

Study day: Study day will be calculated using study day 1 as the reference starting day. For observations on or after study day 1, the below formulae will be used:

Study day = date of observation – date of study day 1 + 1

For observations before study day 1, the formulae below will be used:

Study day = date of observation - date of study day 1

Study week: Study week will be calculated for study day >0 using the below formulae:

CEIL is a function in SAS that round up the value to the nearest integer. The calculation would follow the schedule of activities in the protocol (see Section 1.3 in protocol) where day 29 and day 85 with a plus 7-day visit window are specified for week 4 and 12 respectively. This would therefore calculate study day 1 to 7 as study week 0.

Time to event: The start date of treatment for treated participants or the randomization date for randomized participants who did not take study treatment will be used as the start date for the calculation of time to event. Therefore, the time of event will be defined as "date of event – start of treatment date (for treated participants) / randomization date (for randomized but not treated participants) +1".

Unscheduled assessments: Extra assessments (e.g., laboratory data or vital signs) associated with non-protocol visits will be included in listings, but not in the summary tables, unless otherwise specified.

4.1.3 Intercurrent Events (ICEs)

Important ICEs for this study are detailed in Table 1-2 and will be reviewed prior to study unblinding. Further details regarding the identification of ICEs are provided in Section 6.4.

For each ICE, the number of participants with an ICE will be summarized by week and by study treatment and overall. A participant may have more than one ICE and/or more than one occurrence of the same ICE. All ICEs observed will be summarized.

Boxplots of the observed WASO value separately for participants with no ICEs and participants with ICEs will be produced by visit and study treatment.

Version 2.0 Page: 19 of 57

4.2 Primary Endpoint Analysis

4.2.1 **Definition of Endpoint(s)**

The primary endpoint is the change from baseline in WASO at week 4 as measured by PSG. See Section 6.2.1 for more details on the definition of WASO as measured by PSG.

PSG assessments will be performed on 2 consecutive nights during screening, at week 4 and at week 12. The baseline WASO value will be the mean value of the 2 consecutive nights at screening. Similarly, the week 4 value will be the mean value of the 2 consecutive nights at week 4. If a participant only had one PSG night for a given visit, the data from the one night will be used for the analysis.

Scheduled PSG assessments will be used but in case no scheduled assessment is available, unscheduled assessments while the participants are on treatment will be used and mapped with the following visit windows:

• if the unscheduled PSG fall within study day 22 to 45, then the assessment will be mapped to week 4. Likewise, if the unscheduled PSG fall within study day 78 to 103, then the assessment will be mapped to week 12.

If the participant discontinues treatment prematurely, the same visit windows will be used to map the EoT PSG assessment to the corresponding visit. EoT PSG assessments not mapped to week 4 or week 12 will be summarized together in the descriptive statistics but will be excluded from the model-based analysis.

When deriving study day, if the start time of the PSG recording is on or before 11:00, then the date of recording -1 will be used as the date of observation.

The change from baseline in WASO to week 4 will be calculated as below:

Change from baseline = WASO mean value at week 4 – WASO mean value at baseline

The secondary endpoint, change from baseline in WASO at week 12 as measured by PSG, will be calculated analogous to the primary endpoint.

4.2.2 Main Analytical Approach

The primary estimand to answer the clinical question of the study is described in Section 1.1.

Analyses will be performed using the FAS.

The actual and change from baseline in WASO will be summarized using descriptive statistics by study treatment and week. The change from baseline over time by study treatment will be shown using line plots for means and 95% CI. In addition, descriptive statistics for actual values and change from baseline in WASO will be summarized by study treatment and individual nights (i.e., baseline night 1, baseline night 2, week 4 night 1, week 4 night 2, week 12/EoT night 1).

The descriptive statistics for the actual and change from baseline in WASO by study treatment and week will also be summarized using the SLAS.

The change from baseline in WASO at week 4 and 12 will be analyzed using a MMRM with baseline value, study treatment, average weekly frequency of moderate-to-severe HFs (actual stratification factor <35 moderate to severe HFs per week, ≥35 –<50 moderate to severe HFs per week) and week included as covariates in the

Version 2.0 Page: 20 of 57

model as well as the interaction term study treatment-by-week. An unstructured covariance structure will be used. If convergence cannot be attained, alternative structures will be attempted.

The LSM and standard error for each study treatment and the LSM difference of elinzanetant compared to placebo with corresponding 90% CI will be estimated from the model at week 4 and 12. Line plots of the LSM and 90% CI will be provided by study treatment and visit.

Model description including SAS code are provided in Table 4-2. SAS estimates the standard LSM over a balanced population by assigning equal weights to each category of the categorical covariates specified in the CLASS statement. The OBSMARGIN option within the LSMEANS statement will be specified to adjust the LSM according to the baseline distribution of the class covariates in the data.

Table 4-2: MMRM Model Description

Table 4-2: MINIKWI Model Description		
Dependent variable:	change from baseline in WASO at week 4 and week 12	
Covariates	baseline WASO	
(continuous variables):		
Factors	treatment, week, average weekly frequency of HFs (stratification factor)	
(class variables):		
Interaction terms:	treatment*week	
Covariance structure:	Unstructured (UN)	
	If convergence cannot be attained with the unstructured correlation matrix, the following alternative structures will be attempted in the specified order: autoregressive(1) (AR(1)), and compound symmetry (CS). The first structure in this list with which the model converges will be used. If AR(1) structure is used, a random subject intercept will also be included in the model. If multiple imputation (MI) is performed, then this will need to be applied for each imputed dataset (see Section 4.2.2.1).	
Equation		
1	$Y_{ijkl} = \mu + \beta x_i + t_k + r_l + v_j + (tv)_{jk} + s_i + \varepsilon_{ijkl}$	
	where Y_{ijkl} is the change from baseline in WASO to week j for subject i (with treatment	
	k and baseline average weekly frequency of HFs l),	
	μ is the intercept,	
	β is the baseline covariate effect (baseline coefficient), x_i is the baseline WASO for subject i ,	
	t_{L} is the fixed effect of treatment k ($k=Elinzanetant$, $placebo$),	
	r_{l} is the fixed effect of average weekly frequency of HFs l	
	$(l=<35 \text{ moderate to severe HFs per week}, \ge 35-<50 \text{ moderate to severe HFs per week}, \ge 50 \text{ moderate to severe HFs per week}, v_i \text{ is the fixed effect of week } j (j=4, 12),$	
	$(tv)_{jk}$ is the interaction effect of treatment k by week j,	
	$s \sim \text{Normal } (0, \sigma_s^2) \text{ is the random effect of subject } i \text{ (only if } AR(1) \text{ covariance structure}$	
	is used),	
	$\varepsilon_{ijkl} \sim \text{Normal } (0, \sigma^2)$ represents the residual variance component with	
	$\operatorname{corr}\left(\varepsilon_{ij},\varepsilon_{ij}\right)=\rho_{jj},j\neq j'.$	

Version 2.0 Page: 21 of 57

SAS code:	PROC MIXED data=DATA method=ML;
	CLASS subject treatment average_HF week; MODEL change = baseline treatment average_HF week treatment*week /ddfm=KR outp=resid s; REPEATED week / subject=subject type=un; RANDOM subject; /*only if AR(1) covariance structure is used*/
	LSMEANS treatment*week /alpha=0.1 cl diff obsmargins; ESTIMATE 'Elinzanetant - Placebo at Week 4' treatment 1 -1 treatment*week 1 0 -1 0 /alpha=0.1 cl; ESTIMATE 'Elinzanetant - Placebo at Week 12' treatment 1 - 1 treatment*week 0 1 0 -1 /alpha=0.1 cl; ODS OUTPUT TESTS3=TYPE3 eff LSMeans=LSMEAN ESTIMATES=EST;
	RUN;

The assumption of normality in the MMRM will be assessed visually by residual plots (Q-Q plot and plot of residuals against predicted values). If multiple imputation (MI) is applied (see below Section 4.2.2.1), this will be assessed based on the observed data before multiple imputation.

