4.6.4 Subgroup Analyses

Exploratory subgroup analyses using descriptive statistics will be provided for the primary and secondary endpoint change from baseline in WASO at Week 4 and 12 for the following subgroups:

- Average weekly frequency of moderate to severe HF over 14 days prior to respective visit confirmation date for the HF eligibility (<35 moderate to severe HF per week, ≥35 − <50 moderate to severe HF per week, ≥50 moderate to severe HF per week) per actual stratification.
- Region (North America, Europe)
- BMI (<18.5, 18.5 to <25, 25 to <30, ≥ 30 kg/m²)
- WASO as measured by PSG at baseline (quartiles)

If the number of participants is too small (less than 10%) within a subgroup, then the subgroup categories may be redefined prior to unblinding the study.

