There are no data available on the primary endpoint WASO measured by PSG in women with sleep disturbance associated with the menopause. Therefore, the standard deviation used in the sample size calculation is obtained from a study in patients with insomnia disorder (Mignot et al. 2022). Assuming the pooled standard deviation is 33.2 for the change from baseline in WASO at week 4, a total sample size of 70 participants (35 per arm) would give a 90% probability that the 2-sided 90% confidence interval will have a half width of 14.7 minutes or less.

To account for missing data and possible inflation in variability due to missing data imputation, a total of approximately 78 (39 per treatment) will be randomized in a 1:1 ratio to both treatments. Approximately 223 participants will be screened to achieve 78 randomized participants.

Version 2.0 Page: 43 of 57

6. Supporting Documentation

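### The primary MMRM is coded with maximum likelihood instead of REML, so its 90% confidence interval comes out about 3% too narrow

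*SAP*

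**What the plan says.** SAP Table 4-2 gives the SAS code for the main analysis of change in WASO. The estimation method is set in the first line, "PROC MIXED data=DATA method=ML". The model line is "MODEL change = baseline treatment average_HF week treatment*week", with options "ddfm=KR outp=resid s", so Kenward-Roger degrees of freedom are requested. The covariance is unstructured over weeks 4 and 12: "REPEATED week / subject=subject type=un". The interval is two-sided 90%, from "LSMEANS treatment*week /alpha=0.1 cl diff obsmargins".

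The SAP gives no reason for ML, and neither document mentions REML. Protocol Section 9.3.2.2 describes the MMRM without naming an estimation method. SAP Section 4.8, which lists departures from the protocol, does not discuss it.

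SAP Section 2 states that the aim is to estimate the treatment effect and that nothing will be tested. SAP Section 5 sizes the trial on precision: 35 evaluable participants per arm should give a "90% probability that the 2-sided 90% confidence interval will have a half width of 14.7 minutes or less".

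**The concern.** ML ignores the degrees of freedom spent on the fixed effects, so its variance estimate is too small on average. REML corrects for them. In a large trial the difference is negligible, but with about 70 participants it is not.

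The code also works against itself. Kenward-Roger is a small-sample correction developed for REML estimates. It adjusts the standard errors of the fixed effects and the degrees of freedom, but takes the covariance estimate as nearly unbiased. It therefore cannot undo a downward bias in that estimate. SAP Section 4.8 cites the small sample as a reason for dropping the baseline-by-week term, yet the estimator chosen is the one with the small-sample bias.

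The interval for the treatment difference is what this trial delivers, and its width is how the sample size is justified. An interval that is systematically too short overstates the precision achieved and covers the true difference less often than stated.

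The same model gives the Week 12 secondary result (Section 4.3.1.1) and is reused in the first supplementary analysis. It is also used in the second supplementary analysis if normality fails, and on each imputed dataset if imputation is triggered.

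**Working it through.** **Inputs from the documents**
- SD of the Week 4 change 33.2 minutes; 70 evaluable (35 per arm), 78 randomized; target half-width 14.7 minutes with 90% probability (SAP Section 5).
- Two visits with unstructured covariance (Table 4-2).
- Seven estimable fixed effects: intercept, baseline, treatment, week, treatment-by-week, and two for hot-flash stratum. The equation in Table 4-2 has three strata, and Section 4.6.4 also includes "≥50 moderate to severe HF per week) per actual stratification". The text of Section 4.2.2 names only two.

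**Step 1: the plan's own figure.** For a two-sample t interval with the unbiased pooled variance (68 df):

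half-width = t(0.95, 68) × 33.2 × √(2/35) × √(χ²(0.90, 68)/68)

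= 1.6676 × 7.936 × √(83.31/68) = 13.23 × 1.107 = **14.65 minutes**, against 14.7 stated. The probability that the half-width is at most 14.7 is 0.907, against 0.90 stated.

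The figure reproduces with the unbiased variance. Dividing the residual sum of squares by 70 instead of 68, as ML would in this simple case, gives 14.65 × √(68/70) = 14.44. REML matches the planning basis and ML does not.

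**Step 2: approximate size of the bias.** Let p be the number of mean parameters charged to each visit. The ML/REML variance ratio is then about (N − p)/N. Seven parameters shared over two visits give p = 3.5; charging Week 4 in full for intercept, baseline, treatment and two stratum terms gives p = 5. Coverage is that of a nominal 90% t interval shortened by the SE ratio. At N = 70:

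| p | variance ratio | SE ratio | coverage |
|---|---|---|---|
| 3.5 | 66.5/70 = 0.950 | 0.975 | 89.1% |
| 5 | 65/70 = 0.929 | 0.964 | 88.7% |

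**Step 3: simulation of the Table 4-2 model.** ML and REML were fitted to the same simulated data, with a Kenward-Roger-type standard error and Satterthwaite df for the Week 4 contrast. Assumptions not in the documents: within-participant correlation 0.6, stratum shares 40/30/30%, the missingness shown, and the N = 60 scenario.

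| Scenario | Half-width ML / REML (min) | ML narrower by | Variance ÷ truth, ML / REML | Coverage ML / REML |
|---|---|---|---|---|
| N = 70, complete (3,000 runs) | 12.98 / 13.43 | 3.3% | 0.936 / 0.998 | 89.1% / 90.2% |
| N = 78, 10% missing Week 4, 15% missing Week 12 (1,800 runs) | 12.80 / 13.20 | 3.1% | 0.940 / 1.000 | 89.3% / 90.5% |
| N = 60, 10% missing Week 12 (1,800 runs) | 14.01 / 14.58 | 3.9% | 0.925 / 0.998 | 89.2% / 90.7% |

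The Monte Carlo standard error of coverage is about 0.6 points at 3,000 runs (√(0.89 × 0.11/3000)) and 0.7 at 1,800. The half-width ratios are paired within each dataset and are far more stable.

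**Step 4: does Kenward-Roger rescue ML?** No. At N = 70 the ML/REML ratio of standard errors was 0.968 both with and without the adjustment. ML also produced larger degrees of freedom (71 against 66), which shortens the interval very slightly more.

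**Step 5: sensitivity.** With correlation 0.5, complete data and a t interval on n − 5 df for both methods (5,000 runs per size), ML was 3.6%, 3.1% and 2.8% too narrow at n = 60, 70 and 78. Coverage was 88.3%, 88.5% and 88.8% under ML, against 89.6%, 89.7% and 89.6% under REML. At n = 70 the SE ratio was 0.969 with three hot-flash levels and 0.975 with two.

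**The case against.** The strongest reply is that the effect is small. It is about 0.4 minutes on a half-width of about 13, the point estimate hardly moves, and no test or alpha is involved. SAP Section 4.8 says no meaningful difference has been established for this population, so there is no threshold for 0.4 minutes to cross. Both mean half-widths at 70 participants lie below 14.7, so ML does not manufacture a success on precision. All of this stands, and it bears on how serious the error is, not on whether it is one.

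The coverage figures are also imprecise. In the runs with missing data, ML and REML miss 90% by similar amounts in opposite directions (−0.7 and +0.5 points; −0.8 and +0.7), within or near Monte Carlo error. Those runs alone would not separate ML from nominal. This is fair, and the defensible statement is coverage of about 89%. The firmer evidence is the paired half-width ratio and the variance bias, which agree with the analytic ratio in every scenario.

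The reach is partly conditional. In the main analysis, imputation runs only if more than 5% of the full analysis set lack post-baseline data, and the log-scale analysis runs only if normality fails. Where imputation is used, Rubin's rules add a between-imputation variance that the ML fit within each dataset does not shrink. The 3% should therefore not be carried over; it was not quantified there.

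Finally, the protocol names no estimation method, so ML contradicts nothing in it. That is correct: the fault is in the choice itself, not in a mismatch between documents.

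**Conclusion.** The concern holds: the code is wrong as written. With about 70 participants and the Table 4-2 model, ML understates the Week 4 residual variance by about 6%. The 90% interval is about 3% too narrow (range across the settings examined about 2.5% to 4%), and its coverage is about 89%. The direction is the same in every scenario, and Kenward-Roger does not correct it.

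The error is modest, but it biases the trial's main inferential output in one direction, and no reason is given for it. The treatment estimate and the sample size are not in question.

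The size rests on the planning SD of 33.2 minutes and on assumed values for correlation (0.5 or 0.6), stratum shares and missingness. The Kenward-Roger adjustment was coded outside SAS, so SAS output could differ slightly.

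**What to change.** In SAP Table 4-2, replace `method=ML` with `method=REML` and keep `ddfm=KR`. State in Section 4.2.2 that the MMRM is fitted by REML. Apply the same setting to the Week 12 estimate, both supplementary analyses and any fit to imputed data. Make the change before unblinding. If ML is deliberate, the SAP should say why and acknowledge the effect on the interval.

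The cost is one keyword in the SAP and program, one sentence of text, and a reported interval about 3% wider. The sample size does not change, since the 14.7-minute calculation already assumes the unbiased variance.
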